#### **9.1.5. Study Files and Retention of Records**

The investigator must maintain adequate and accurate records to enable the conduct of the study to be fully documented and the study data to be subsequently verified. These documents should be classified into at least the following two categories: (1) investigator's study file, and (2) subject clinical source documents.

The investigator's study file will contain the protocol/amendments, CRF and query forms, IRB or IEC and governmental approval with correspondence, informed consent, drug records, staff curriculum vitae and authorization forms, and other appropriate documents and correspondence.

The required source data should include sequential notes containing at least the following information for each subject:

- Subject identification (name, date of birth, gender);
- Documentation that subject meets eligibility criteria, ie, history, physical examination, and confirmation of diagnosis (to support inclusion and exclusion criteria);
- Documentation of the reason(s) a consented subject is not enrolled
- Participation in study (including study number);

- Study discussed and date of informed consent;
- Dates of all visits;
- Documentation that protocol specific procedures were performed;
- Results of efficacy parameters, as required by the protocol;
- Start and end date (including dose regimen) of IMP, including dates of dispensing and return;
- Record of all adverse events and other safety parameters (start and end date, and including causality and severity);
- Concomitant medication (including start and end date, dose if relevant; dose changes);
- Date of study completion and reason for early discontinuation, if it occurs.

All clinical study documents must be retained by the investigator until at least 2 years or according to local laws, whichever is longer, after the last approval of a marketing application in an ICH region (ie, United States, Europe, or Japan) and until there are no pending or planned marketing applications in an ICH region; or, if no application is filed or if the application is not approved for such indication, until 2 years after the investigation is discontinued and regulatory authorities have been notified. Investigators may be required to retain documents longer if specified by regulatory requirements, by local regulations, or by an agreement with Gilead. The investigator must notify Gilead before destroying any clinical study records.

Should the investigator wish to assign the study records to another party or move them to another location, Gilead must be notified in advance.

If the investigator cannot provide for this archiving requirement at the study site for any or all of the documents, special arrangements must be made between the investigator and Gilead to store these records securely away from the site so that they can be returned sealed to the investigator in case of an inspection. When source documents are required for the continued care of the subject, appropriate copies should be made for storage away from the site.

#### **9.1.6. Case Report Forms**

For each subject consented, an eCRF will be completed by an authorized study staff member whose training for this function is documented according to study procedures. eCRF should be completed on the day of the subject visit to enable the sponsor to perform central monitoring of safety data. The Eligibility Criteria eCRF should be completed only after all data related to eligibility have been received. Subsequent to data entry, a study monitor will perform source data verification within the EDC system. Original entries as well as any changes to data fields will be stored in the audit trail of the system. Prior to database lock (or any interim time points as described in the clinical data management plan), the investigator will use his/her log in credentials to confirm that the forms have been reviewed, and that the entries accurately reflect

the information in the source documents. The eCRF capture the data required per the protocol schedule of events and procedures. System-generated or manual queries will be issued to the investigative site staff as data discrepancies are identified by the monitor or internal Gilead staff, who routinely review the data for completeness, correctness, and consistency. The site coordinator is responsible for responding to the queries in a timely manner, within the system, either by confirming the data as correct or updating the original entry, and providing the reason for the update (eg, data entry error). At the conclusion of the trial, Gilead will provide the site with a read-only archive copy of the data entered by that site. This archive must be stored in accordance with the records retention requirements outlined in Section 9.1.5.

#### **9.1.7. Investigational Medicinal Product Accountability and Return**

Gilead recommends that used and unused IMP supplies be returned to the shipping facility from which it came for eventual destruction. The study monitor will provide instructions for return. If return is not possible, the study monitor will evaluate each study center's IMP disposal procedures and provide appropriate instruction for destruction of unused IMP supplies. If the site has an appropriate standard operating procedure (SOP) for drug destruction as determined by Gilead QA, the site may destroy used (empty or partially empty) and unused IMP supplies in accordance with that site's approved SOP. A copy of the site's approved SOP will be obtained for central files.

If IMP is destroyed on site, the investigator must maintain accurate records for all IMP destroyed. Records must show the identification and quantity of each unit destroyed, the method of destruction, and the person who disposed of the IMP. Upon study completion, copies of the IMP accountability records must be filed at the site. Another copy will be returned to Gilead.

The study monitor will review IMP supplies and associated records at periodic intervals.

#### **9.1.8. Inspections**

The investigator will make available all source documents and other records for this trial to Gilead's appointed study monitors, to IRB or IEC, or to regulatory authority or health authority inspectors.

#### **9.1.9. Protocol Compliance**

The investigator is responsible for ensuring the study is conducted in accordance with the procedures and evaluations described in this protocol.

### **9.2. Sponsor Responsibilities**

#### **9.2.1. Protocol Modifications**

Protocol modifications, except those intended to reduce immediate risk to study subjects, may be made only by Gilead. The investigator must submit all protocol modifications to the IRB or IEC in accordance with local requirements and receive documented IRB or IEC approval before modifications can be implemented.

## **9.2.2. Study Report and Publications**

A clinical study report (CSR) will be prepared and provided to the regulatory agency. Gilead will ensure that the report meets the standards set out in the ICH Guideline for Structure and Content of Clinical Study Reports (ICH E3). Note that an abbreviated report may be prepared in certain cases.

Investigators in this study may communicate, orally present, or publish in scientific journals or other scholarly media only after the following conditions have been met:

the results of the study in their entirety have been publicly disclosed by or with the consent of Gilead in an abstract, manuscript, or presentation form or the study has been completed at all study sites for at least 2 years

The investigator will submit to Gilead any proposed publication or presentation along with the respective scientific journal or presentation forum at least 30 days before submission of the publication or presentation.

No such communication, presentation, or publication will include Gilead's confidential information (see Section 9.1.4).

The investigator will comply with Gilead's request to delete references to its confidential information (other than the study results) in any paper or presentation and agrees to withhold publication or presentation for an additional 60 days in order to obtain patent protection if deemed necessary.

## **9.3. Joint Investigator/Sponsor Responsibilities**

### **9.3.1. Payment Reporting**

Investigators and their study staff may be asked to provide services performed under this protocol, eg, attendance at Investigator's Meetings. If required under the applicable statutory and regulatory requirements, Gilead will capture and disclose to Federal and State agencies any expenses paid or reimbursed for such services, including any clinical trial payments, meal, travel expenses or reimbursements, consulting fees, and any other transfer of value.

### **9.3.2. Access to Information for Monitoring**

In accordance with regulations and guidelines, the study monitor must have direct access to the investigator's source documentation in order to verify the accuracy of the data recorded in the eCRF.

The monitor is responsible for routine review of the eCRF at regular intervals throughout the study to verify adherence to the protocol and the completeness, consistency, and accuracy of the data being entered on them. The monitor should have access to any subject records needed to verify the entries on the eCRF. The investigator agrees to cooperate with the monitor to ensure that any problems detected through any type of monitoring (central, on site) are resolved.

### **9.3.3. Access to Information for Auditing or Inspections**

Representatives of regulatory authorities or of Gilead may conduct inspections or audits of the clinical study. If the investigator is notified of an inspection by a regulatory authority the investigator agrees to notify the Gilead medical monitor immediately. The investigator agrees to provide to representatives of a regulatory agency or Gilead access to records, facilities, and personnel for the effective conduct of any inspection or audit.

### **9.3.4. Study Discontinuation**

Both the sponsor and the investigator reserve the right to terminate the study at any time. Should this be necessary, both parties will arrange discontinuation procedures and notify the appropriate regulatory authority(ies), IRBs, and IECs. In terminating the study, Gilead and the investigator will assure that adequate consideration is given to the protection of the subjects' interests.

## 11. APPENDICES

- Appendix 1. Investigator Signature Page
- Appendix 2. Study Procedures Table
- Appendix 3. GSI Grading Scale for Severity of Adverse Events and Laboratory Abnormalities
- Appendix 4. Pregnancy Precautions, Definition for Female of Childbearing Potential, and Contraceptive Requirements

**Appendix 2. Study Procedures Table**

**Appendix Table 1. Screening, On-Treatment Visits**

Clinical Assessments	Screening	Pre-Surgery (if more than 48 hours from screening to transplant)	Day 1 a	Days on Treatment (±2 days)						ET/ Unscheduled e
				3	5	7	14	21	28	
Informed Consent	X									
Determine Eligibility	X	X								
Medical History	X	X								
Physical Examination	X	X								X
Height and Weight b	X	X	X							X
Vital Signs c	X	X	X	X	X	X	X	X	X	X
12-lead ECG d	X	X								
CPT and MELD Scores	X	X								
Adverse Events and Concomitant Medications	X	X	X	X	X	X	X	X	X	X
Pregnancy Prevention Counseling	X	X	X							X
Hematology & Chemistry	X	X	X	X	X	X	X	X	X	X
Coagulation (PT, PTT and INR)	X	X	X	X	X	X	X	X	X	X
CrCL calculation	X	X	X	X	X	X	X	X	X	X
HCV RNA (Plasma) e	X	X	X	X	X	X	X	X	X	X
Viral RNA Sequencing /Phenotyping Sample (Plasma)			X	X	X	X	X	X	X	X
Single Pharmacokinetic Sample						X	X	X	X	X
Pregnancy Testing f	X	X	X						X	X
Urinalysis	X	X								

Clinical Assessments	Screening	Pre-Surgery (if more than 48 hours from screening to transplant)	Day 1 a	Days on Treatment (±2 days)						ET/ Unscheduled c
				3	5	7	14	21	28	
IL28B Genotype			X							
HCV Genotype	X									
HCV, HIV, HBV Serology	X	X								
Archive Sample g			X						X	X
PPD										
PK Sub-study Collection i			X							
Study Drug Dosing			X	X	X	X	X	X	X	
Review of Study Drug Adherence and Drug Accountability j				X	X	X	X	X	X	X

- a If the transplant is completed before noon, the subject will take their first dose that day after the transplant which will be considered Day 1. If the transplant is completed after noon, the subject will take their first dose the following morning which will be considered Day 1. The planned first dose may be delayed for up to 1 day if, in the investigators opinion, delay is in the subject's medical interest. ET = Early Termination; at all unscheduled visits initiated for the purpose of confirmatory testing, a viral sequence analysis plasma sample must be obtained.
- b Weight should be done with inner clothing and without shoes and Height should be done at screening only. Height will be performed only at initial screening visit. Weight will be assessed at screening and Day 1 for CrCL calculations. CrCL calculation for all post-transplant visits will use the Day 1 weight.
- c Vital signs include resting blood pressure, pulse, respiratory rate and temperature.
- d Subjects will be required to rest in a supine position for ≥ 5 minutes prior to making a recording. The investigator (or qualified designee) should review the ECG traces recorded in real time for gross abnormalities.
- e HCV RNA samples will be collected at all visits. An additional HCV RNA sample will be collected just before but as close to the transplant as possible.
- f For females of childbearing potential only: serum β-hCG at Screening, urine test thereafter. If urine is positive, confirm immediately with serum β-hCG. .

## PPD

### PPD

- i All subjects will have intensive serial PK samples drawn before the SOF/VEL dose on Day 1, then dose is given, then remaining samples are collected for 24hrs. The 24 hr sample should be collected before the dose of study drug on Day 2. Detailed instructions will be provided to each study site and will also be included in the lab manual.
- j Study drug will be reconciled at every post-Day 1 visit by the investigator in order to monitor the subject's adherence with the dosing regimen. Subjects must be instructed to bring back all bottles of study drug in the original container at every post Day 1 study visits through the end of treatment.

**Appendix Table 2. Post-Treatment Study Visits**

Clinical Assessments a	Visit identified by Post-Treatment study week			
	Post-Treatment Week 1 (± 3 days)	Post-Treatment Week 2 (± 3 days)	Post-Treatment Week 4 (± 5 days)	Post-Treatment Week 12 (±5 days)
Weight and Vital Signs b			X	
Adverse Events and Concomitant Medications	X	X	X	
Pregnancy Prevention Counseling	X			
Hematology & Chemistry	X	X	X	X
Coagulation (PT, PTT and INR)	X	X	X	X
HCV RNA and Viral Sequencing Sample (Plasma)	X	X	X	X
Pregnancy Testing c	X	X	X	

a If a subject is in Post-treatment follow-up and undergoes liver transplant, they will continue the follow-up schedule.

b Weight should be done with inner clothing and without shoes. Vital signs include resting blood pressure, pulse, respiratory rate and temperature.

c For females of childbearing potential only: serum β-hCG at Screening, urine test thereafter. If urine is positive, confirm immediately with serum β-hCG.

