**Criteria for Evaluation:**

**Safety:** AEs and safety laboratory tests will be collected throughout the study (through the Post-treatment week 4 visit).

**Efficacy:** Efficacy will be evaluated using scheduled assessments of HCV RNA performed using Roche COBAS® AmpliPrep/COBAS® TaqMan® HCV Test, v. 2.0.

**Pharmacokinetics:** A single PK blood sample will be collected at each on-treatment visit for all subjects except on Days 1, 3 and 5.

All subjects will be required to participate in an intensive serial PK sub-study to be performed on Day 1. The PK of SOF (and its metabolites GS-566500 and GS-331007), and VEL will be assessed. Serial PK samples will be collected at the following time points: 0 (pre-dose), 0.5, 1, 2, 4, 8, 12 and 24 hours post-dose.

---

---

**Statistical Methods:** The primary efficacy endpoint is the percentage of subjects who achieve SVR12 (HCV RNA < lower limit of quantitation [LLOQ] 12 weeks after stopping study drug) for subjects in the Full Analysis Set (FAS).

Secondary efficacy endpoints include the percentage of subjects who attain SVR at 4 weeks after cessation of treatment (SVR4); the percentage of subjects who have HCV RNA <LLOQ at each on-treatment visit; and the percentage of subjects with virologic failure (VF, defined as HCV RNA  $\geq$  LLOQ at end of treatment or relapse during the Post-treatment follow-up period).

The primary safety endpoint is the percentage of subjects who discontinue from study drug due to an adverse event. Deaths, graft loss, and rejection episodes will also be listed or summarized, as appropriate.

Other endpoints of interest include changes to immunosuppressive therapy and the emergence of viral resistance to SOF or VEL during and after cessation of treatment, and HCV RNA levels (IU/mL) at each on-treatment visit, if relevant.

---

This study will be conducted in accordance with the guidelines of Good Clinical Practice (GCP) including archiving of essential documents.

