#### **6.6. Post-Treatment Assessments**

Post-treatment Weeks 1, 2, 4, and 12 visits must be scheduled from the date of the last dose of study drug.

Subjects who have HCV RNA  $\leq$ LLOQ at end of treatment and do not relapse will complete all post-treatment visits at Weeks 1, 2, 4, and 12. Subjects that experience relapse will have confirmatory testing as soon as possible and will not be required to complete additional visits.

If a subject must undergo a second transplantation while on study treatment or is relisted for transplantation, all study treatment must be stopped.

If a subject is in the Post-treatment follow-up and undergoes a second liver transplant, the subject will continue with the follow-up visits from the first transplantation (for the assessment of Post-transplant recurrence). If the subject is more than 4 weeks after the last dose of study drug at the time of the second transplant and had completed the safety follow-up period, it is not necessary to resume adverse event collection.

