#### Adverse Events

All AEs, except those described in Section 7.5, regardless of cause or relationship, that occur from initiation of study medication until 30-days after last administration of study drug must be reported to the eCRF database as instructed.

All AEs should be followed up until resolution or until the adverse event is stable, if possible. Gilead Sciences may request that certain AEs be followed beyond the protocol defined follow up period.

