#### Serious Adverse Events

All SAEs, except those described in Section 7.5, regardless of cause or relationship, that occur from initiation of study medication until 30 days after last administration of study drug, must be reported to the eCRF database and Gilead Drug Safety and Public Health (DSPH) as instructed. This also includes any SAEs resulting from protocol-associated procedures performed after informed consent is signed.

Investigators are not obligated to actively seek SAEs after the protocol defined follow up period ;however, if the investigator learns of any SAEs that occur after study participation has

concluded and the event is deemed relevant to the use of IMP, he/she should promptly document and report the event to Gilead DSPH.

All AEs and SAEs will be recorded in the eCRF database within the timelines outlined in the eCRF completion guideline.

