7.1.5. Treatment-Emergent Adverse Events

7.1.5.1. Definition of Treatment-Emergent

Treatment-emergent adverse events (TEAEs) are defined as 1 or both of the following:

- Any AEs with an onset date on or after the study drug start date and no later than 30 days after permanent discontinuation of study drug
- Any AEs leading to premature discontinuation of study drug

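### The last scheduled adverse-event review can fall up to 7 days before the end of the 30-day post-dose window in which events are counted

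*Protocol*

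**What the plan says.** All days here are counted from the last dose, not as study days.

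**Schedule.** Appendix Table 2 of the protocol has a row for "Adverse Events and Concomitant Medications". It is marked at post-treatment Weeks 1, 2 and 4 and blank at Week 12. The Week 4 column is headed "Post-Treatment Week 4 (± 5 days"). Section 6.6 fixes the anchor: "Post-treatment Weeks 1, 2, 4, and 12 visits must be scheduled from the date of the last dose of study drug".

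**Collection.** Section 7.3 covers AEs "that occur from initiation of study medication until 30-days after last administration of study drug must be reported to the eCRF database". For serious AEs the same section says "until 30 days after last administration of study drug, must be reported to the eCRF database". Section 5.3 also records concomitant medications to 30 days after the last dose.

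**Analysis.** Protocol Sections 8.2.1.2, 8.6 and 8.6.2 carry safety summaries to the last dose plus 30 days. SAP Section 7.1.5.1 counts an AE as treatment-emergent if its onset is "no later than 30 days after permanent discontinuation of study drug".

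**Places with a different end point.** The synopsis, under Criteria for Evaluation, says "AEs and safety laboratory tests will be collected throughout the study (through the Post-treatment week 4 visit"). The synopsis text on study procedures likewise places AE and medication review only through post-treatment Week 4. Section 6.6, on second transplants during follow-up, links completion of safety follow-up to a point more than 4 weeks after the last dose.

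**The concern.** The window in which events are counted and the visits at which subjects are asked about events do not end together. A subject seen early in the Week 4 window has no later scheduled contact that asks about AEs, although events in the remaining days belong in the treatment-emergent tables. A site that follows the synopsis would regard collection as finished at that visit; a site that follows Section 7.3 would not.

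Safety and tolerability is one of the two primary objectives. SAP Section 7.1.6 reports the number and percentage of subjects with each event and does not adjust for how long each subject was actually asked. With about 10 subjects, one subject whose only event of a given type is missed moves that percentage by 1/10, or 10 points.

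**Working it through.** **Inputs**

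- Week 4 visit window: ±5 days (Appendix Table 2), from the last dose (Section 6.6).
- End of AE collection and counting: Day 30 (Protocol 7.3, 8.2.1.2, 8.6.2; SAP 7.1.5.1).
- Next scheduled visit: Week 12 ±5 days, with no AE review (Appendix Table 2).

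**Check that Week 4 means Day 28.** SAP Section 3.8.2 defines the follow-up day as collection date minus last dose date. A footnote to its Table 2 puts the lower bounds for HCV RNA 7 days before the Week 4 target and 14 days before the Week 12 target. This gives 4 × 7 − 7 = 21 and 12 × 7 − 14 = 70. The table states 21 and 70, so Week 4 is Day 28 and Week 12 is Day 84.

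**Permitted visit days.** Earliest 28 − 5 = Day 23; latest 28 + 5 = Day 33; 11 permitted days in all.

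**Days without a scheduled AE review** = max(0, 30 − visit day):

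| Week 4 visit on day | 23 | 24 | 25 | 26 | 27 | 28 | 29 | 30–33 |
|---|---|---|---|---|---|---|---|---|
| Days not covered | 7 | 6 | 5 | 4 | 3 | 2 | 1 | 0 |

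Seven of the 11 permitted days leave a gap. The largest is 7/30 = 23% of the post-dose window; the nominal visit leaves 2/30 = 7%. These shares describe the calendar only. They are not denominators in any planned table.

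**Next contact.** Week 12 is Day 84 − 5 = 79 at the earliest. An event with onset on Day 30, first asked about on Day 84, would need recall over 54 days, or about 8 weeks.

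**Subjects who leave early.** Section 6.6 releases subjects who relapse from further visits after confirmatory testing, and SAP Section 1.2 discontinues subjects with confirmed virologic failure. Sections 3.7 and 6.8 instead keep subjects who terminate early for quantifiable HCV RNA until Week 4. On the Section 6.6 reading, a relapse found at the Week 2 visit (14 ± 3, Days 11 to 17) would leave 30 − 17 = 13 to 30 − 11 = 19 days after that visit. A confirmatory unscheduled visit would shorten this, because Section 6.5 requires AE information at such visits. The documents do not settle which reading applies.

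**The case against.** The strongest reply is that collection to Day 30 is already mandatory. Section 7.3 requires events "that occur from initiation of study medication until 30-days after last administration of study drug must be reported", whatever the visit dates. AEs are followed to resolution or stability where possible, unscheduled visits must record them, and nothing prevents a site from entering at Week 12 an event that began by Day 30. A ±5-day window is ordinary tolerance, 7 days is the worst case, and 4 of the 11 permitted days leave no gap.

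Most of this stands. A reader might infer that events after an early Week 4 visit are excluded from the analysis, or that the tables will certainly under-count. The documents support neither: the collection rule and the definition of treatment-emergent both reach Day 30, and no event rate is given from which to estimate a number missed. A reader might also express the gap as a share of total time at risk, but the SAP plans no person-time rates. With one arm, no between-group bias can arise.

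The reply does not remove two things. A duty to report an event once known is not a scheduled occasion for asking about it. And the synopsis gives sites a different end of collection from Section 7.3.

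**Conclusion.** The mismatch is real and small. For a Week 4 visit on Days 23 to 29, between 1 and 7 days of the 30-day window have no scheduled AE review, with 2 days at the nominal visit. Treatment-emergent AE and serious AE counts may therefore be under-ascertained at the end of the window. By how much cannot be said from the documents; it depends on actual visit dates and on how many events subjects would not volunteer.

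Two main safety outputs are essentially untouched. The primary safety endpoint is stopping study drug early because of an AE, and an event that begins after the last dose cannot change it. All deaths observed during the study are summarised whether or not they are treatment-emergent (SAP 7.1.6).

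The conclusion assumes that sites use the permitted visit window and make no contact beyond the schedule. It calls for a cheap improvement and a wording correction; it does not show that the planned safety tables are invalid.

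**What to change.** Add a telephone contact for AEs and concomitant medications at or just after 30 days post-dose, for every dosed subject whose last AE review falls before Day 30. State that this includes subjects released early for relapse or virologic failure. Then reconcile the two synopsis statements and the second-transplant paragraph of Section 6.6 with the 30-day rule in Section 7.3.

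Two alternatives are weaker. An AE question at Week 12, limited to onset by Day 30, misses subjects who leave early and depends on about 8 weeks of recall; it serves only as a back-up. Moving the Week 4 visit to Days 30 to 33 would close the gap for subjects who attend, but SAP Table 2 ends the safety laboratory and vital-sign windows at Day 30, so values from Days 31 to 33 would drop out of those summaries.

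The cost is one short call per affected subject, at most about 10 in total, with no change to dosing, endpoints or sample size.
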